## 4.2 Event Monitoring/Survival Follow-up

|                  | Event Monitoring Phase* |       |                         |       |                    |
|------------------|--------------------------------|-------|-------------------------|-------|--------------------|
|                  | Every 3 months until PD        | At PD | After PD every 6 months | Death | New Primary        |
| Event Monitoring | X                              | X     | X                       | X     | At each occurrence |

\*If a patient is still alive 2 years after registration, no further follow-up is required.

## 5.0 Grouping Factor

Phase: Phase I vs. Phase II

## 6.0 Pre-registration/Registration Procedures

### 6.1 Pre-Registration (Step 1)

6.11 Phase I: Prior to discussing protocol entry with the patient, call the MCCC Registration Office at [REDACTED] for dose level and to ensure that a place on the protocol is open to the patient.

6.12 Phase II: To pre-register a patient, access the Mayo Clinic Cancer Center (MCCC) web page and enter the registration/randomization application. The registration/ randomization application is available 24 hours a day, 7 days a week. Back up and/or system support contact information is available on the website. If unable to access the website, call the MCCC Registration Office at [REDACTED] between the hours of 8 a.m. and 5:00 p.m. Central Time (Monday through Friday).

The instructions for the registration/randomization application are available on the MCCC web page [REDACTED] detail the process for completing and confirming patient registration. Prior to initiation of protocol treatment, this process must be completed in its entirety and an MCCC subject ID number must be available as noted in the instructions. It is the responsibility of the individual and institution registering the patient to confirm the process has been successfully completed prior to release of the study agent. Patient registration via the registration/randomization application can be confirmed in any of the following ways:

- Contact the MCCC Registration Office [REDACTED]. If the patient was fully registered, the MCCC Registration Office staff can access the information from the centralized database and confirm the registration.
- Refer to “Instructions for Remote Registration” in section “Finding/Displaying Information about A Registered Subject.”

6.13 Prior to accepting the pre-registration, the registration/randomization application will verify the following:

- IRB approval at the registering institution
- Patient pre-registration eligibility
- Existence of a signed consent form
- Existence of a signed authorization for use and disclosure of protected health information.

6.14 A mandatory correlative research component is part of this study, the patient will be automatically registered onto this component (see Sections 3.29c and 17.1).

### 6.2 Registration Requirements (Step 2):

6.21 Phase I: To register a patient, fax [REDACTED] a completed eligibility checklist to the Mayo Clinic Cancer Center (MCCC) Registration Office between 8 a.m. and 4:30 p.m. central time Monday through Friday.

6.22 Phase II: To register a patient, access the Mayo Clinic Cancer Center (MCCC) web page and enter the registration/randomization application. The

registration/randomization application is available 24 hours a day, 7 days a week. Back up and/or system support contact information is available on the Web site. If unable to access the Web site, call the MCCC Registration Office at [REDACTED] [REDACTED] between the hours of 8 a.m. and 4:30 p.m. Central Time (Monday through Friday).

The instructions for the registration/randomization application are available on the MCCC web page [REDACTED] and detail the process for completing and confirming patient registration. Prior to initiation of protocol treatment, this process must be completed in its entirety and a MCCC subject ID number must be available as noted in the instructions. It is the responsibility of the individual and institution registering the patient to confirm the process has been successfully completed prior to release of the study agent. Patient registration via the registration/randomization application can be confirmed in any of the following ways:

- Contact the MCCC Registration Office [REDACTED]. If the patient was fully registered, the MCCC Registration Office staff can access the information from the centralized database and confirm the registration.
- Refer to “Instructions for Remote Registration” in section “Finding/Displaying Information about A Registered Subject.”

#### 6.23 Phase I and II

6.231 Documentation of IRB approval must be on file in the Registration Office before an investigator may register any patients.

In addition to submitting initial IRB approval documents, ongoing IRB approval documentation must be on file (no less than annually) at the Registration Office [REDACTED]. If the necessary documentation is not submitted in advance of attempting patient registration, the registration will not be accepted and the patient may not be enrolled in the protocol until the situation is resolved.

When the study has been permanently closed to patient enrollment, submission of annual IRB approvals to the Registration Office is no longer necessary.

6.232 At the time of registration, Registration/Randomization Application will verify the following:

- IRB approval
- Patient eligibility
- Existence of a signed consent form

6.233 At the time of registration, the following will be recorded:

- Patient has/has not given permission to store and use his/her sample(s) for future research at Mayo.
- Patient has/has not given permission to store and use his/her sample(s) for future research to learn, prevent, or treat other health problems.

6.234 Correlative Research

A mandatory correlative research component is part of this study, the patient will automatically be registered onto this component (see Section 14).

An optional correlative research component is part of this study, there will be an option to select if the patient is to be registered onto this component (see Section 17.0).

- Patient has/has not given permission to give his/her recurrence tissue sample for research testing
- 6.235 Consent and treatment on this protocol must commence at Mayo Clinic Rochester, Mayo Clinic Florida, or Mayo Clinic Arizona under the supervision of a medical oncologist.
- 6.236 Treatment cannot begin prior to registration and must begin  $\leq 28$  days after registration.
- 6.237 Screening tests/procedures (see Section 4.0) must be completed within the guidelines specified on the test schedule.
- 6.238 All required baseline symptoms (see Section 10.6) must be documented and graded.
- 6.239 Study drug is available on site

## 7.0 Protocol Treatment

### 7.1 Phase I Treatment Schedule

Use actual weight or estimated dry weight if fluid retention

#### 7.11 Treatment table

| Number of Patients | Cohort Level | Anetumab ravtansine (mg/kg) Q3W IV | Atezolizumab (mg) Q3W IV |
|--------------------|--------------|------------------------------------|--------------------------|
| 3-6                | -1           | 4.5                                | 1200 mg                  |
| 3-6                | 1*           | 5.5                                | 1200 mg                  |
| 3-6                | 2            | 6.5                                | 1200 mg                  |

\*Starting dose

### 7.2 Determination of Maximum Tolerated Dose (MTD)

In Phase I, dose escalation of anetumab ravtansine in combination with Atezolizumab will be performed according to the standard 3+3 design of dose cohorts. Dose escalation decisions will be based on the incidence of Treatment Emergent Adverse Events (TEAEs) observed after Cycle 1 (C1) that fulfills the criteria for a DLT. If a clinically significant TEAE related to anetumab ravtansine is observed more frequently after C1, then this event may be declared a DLT at the investigators' discretion in consultation with the sponsor. If a clinically significant TEAE related to atezolizumab is observed more frequently, or with greater severity than what has been reported in the prescribing information or in the literature, this event also may be declared a DLT at the discretion of investigators in consultation with the sponsor.

At least 3 subjects in each cohort need to provide sufficient safety data after the first treatment cycle (21 days) before a decision can be made whether it is safe to proceed to the next dose level of anetumab ravtansine. To be evaluable for a dose escalation decision, subjects must complete one treatment cycle in their assigned dose cohort; receive one complete infusion of each treatment (anetumab ravtansine and atezolizumab). If a DLT occurs in 2 out of 3 subjects at a given dose level (or in 2 of 4 subjects, if the 4th subject has been enrolled), or in 2 out of up to 6 subjects in the Phase II portion at a given dose level, then dose escalation will stop and the current dose will be declared the non-tolerable dose.

### 7.3 Patient Must Return to Treating Institution During Study Treatment

For this protocol, the patient must return to the treating institution for all visits during study treatment.

### 7.4 Clinically Indicated Treatment or Supportive Care by a Local Medical Doctor

Clinically indicated treatment or supportive care by a local medical doctor (LMD) is not allowed throughout the study.

### 7.5 Reporting of DLTs

Investigators are to contact the Study Chair as soon as any dose-limiting toxicity (DLT) occurs.

#### 7.6 Definition of DLT

Dose-limiting toxicity (DLT) will be defined as an AE occurring in Cycle 1 of the study, attributed (definitely, probably, or possibly) to treatment and meeting the following criteria:

- Grade 4 ANC  $\geq 7$  days or  $\geq$ Grade 3 ANC of any duration with fever  $> 38.3^{\circ}\text{C}$ .
- Grade 4 platelet count or Grade 3 platelet count associated with bleeding.
- AST/ALT/ alkaline phosphatase  $\geq$  Grade 3 if total bilirubin  $< 1.5 \times \text{UNL}$ .
- AST/ALT/alkaline phosphatase  $\geq 2.5 \times \text{UNL}$  together with  $\geq$  Grade 2 total bilirubin ( $> 1.5 \times \text{UNL}$ ).
- Other  $\geq$  Grade 3 non-hematologic toxicities (except transient asymptomatic electrolyte abnormality and nausea, vomiting or diarrhea untreated with anti-emetic support or anti-diarrheal agents, respectively).

Grade 3 laboratory abnormalities without clinically significant sequel (e.g., amylase elevation, etc) will NOT be considered DLT.

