#### 8.12 Nonhematological TEAEs requiring treatment modification of any or all agents of study treatment

- CTCAE Grade 4 non-hematologic toxicity
- CTCAE Grade 3 non-hematologic toxicity that, in the investigator's opinion, warrants treatment modification excluding the following:
  - CTCAE Grade 3 nausea, vomiting, or diarrhea if manageable with antiemetic or antidiarrheal agents within 7 days would not require treatment modification
  - CTCAE Grade 3 fatigue lasting  $\leq 72$  hours would not require treatment modification
  - Certain asymptomatic CTCAE Grade 3 laboratory abnormalities without a clear clinical correlate, if the investigator determines that this TEAE would not require treatment modification.
  - Grade 3 corneal epitheliopathy according to the Bayer Severity Grading that, in the investigator's opinion, warrant treatment modification.
- Grade 2 corneal epitheliopathy according to the Bayer Severity Grading that, in the investigator's opinion, warrants treatment modification.
- CTCAE Grade  $\geq 2$  neurotoxicity
- AST and/or ALT increase  $> 3.0 \times \text{ULN}$  (CTCAE Grade  $\geq 2$ ) with concomitant increase in total bilirubin  $> 1.5 \times \text{ULN}$  (CTCAE Grade  $\geq 2$ ). For patients with liver metastases, AST/ALT increase  $> 5.0 \times \text{ULN}$  with concomitant increase in total bilirubin  $> 2.0 \times \text{ULN}$

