#### **8.17 Anetumab ravtansine dose adjustments in response to neutrophil and platelet nadir counts of the previous cycle:**

| CTCAE System/Organ/Class (SOC)       | GRADE   | ADVERSE EVENT   | AGENT               | ACTION**              |
|--------------------------------------|---------|---|---------------------|-----------------------|
| INVESTIGATIONS                       | Grade 2 | Neutrophil count decrease >500 or <500 for <7 days AND Platelet count decreased $\geq$ 25,000   | Anetumab ravtansine | No change             |
| INVESTIGATIONS                       | Grade   | Neutrophil count decrease <500 for $\geq$ 7 days AND Platelet count decreased <25,000 for $\geq$ 7 days with or without active bleeding, OR <50,000 for $\geq$ 7 days with clinically significant bleeding b | Anetumab ravtansine | Decrease 1 dose level |
| BLOOD AND LYMPHATIC SYSTEM DISORDERS | Grade 3 | Febrile neutropenia AND Platelet count <25,000 for $\geq$ 7 days with or without active bleeding, OR <50,000 for $\geq$ 7 days with clinically significant bleeding b  |                     | Decrease 1 dose level |

a Anetumab ravtansine dose reduction by 1 dose level translates to a change from 6.5 mg/kg (BW) Q21D to 5.5 mg/kg Q21D, or from 5.5 mg/kg Q21D to 4.5 mg/kg Q21D.

b Clinically significant bleeding is that which requires platelet transfusion.

c Febrile neutropenia is defined as ANC < 500 with fever of  $>38.3^{\circ}\text{C}$  [ $101^{\circ}\text{F}$ ] or a sustained body temperature of  $\geq 38.0^{\circ}\text{C}$  [ $100.4^{\circ}\text{F}$ ] for more than one hour).

If anetumab ravtansine treatment modification is required due to a nonhematological TEAE, and the continuation of anetumab ravtansine treatment is appropriate at the investigator's discretion, then the anetumab ravtansine dose will be reduced after CTCAE Grade 4 nonhematologic TEAE and Bayer Grade 3 corneal epitheliopathy, or either reduced or maintained at the investigator's discretion after CTCAE Grade 3 non-hematologic TEAE or Bayer Grade 2 corneal epitheliopathy change (attached table).

The anetumab ravtansine dose reduction due to nonhematological TEAEs will be performed by 1 mg/kg Q21D as appropriate, i.e., from 6.5 mg/kg Q21D to 5.5 mg/kg Q21D, or from 5.5 mg/kg Q21D to 4.5 mg/kg Q21D.

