- AST or ALT  $>5\times$ ULN or total bilirubin  $>3\times$ ULN
- Grade 4 diarrhea or colitis
- Grade 4 hypophysitis
- Any grade myasthenic syndrome/myasthenia gravis, Guillain-Barré, or meningoencephalitis
- Grade 3 or 4 ocular inflammatory toxicity
- Grade 4 or any grade of recurrent pancreatitis
- Grade 3 or 4 infusion-related reactions
- Grade 4 rash

Treatment may, under limited and compelling circumstances, be resumed in patients who have recovered from the following events after consultation with the trial Principal Investigator:

- Grade 2 pneumonitis
- Grade 2 ocular inflammatory toxicity
- Grade 2 infusion-related reactions

For detailed information regarding management of adverse events associated with atezolizumab, please refer to the most current version of the Atezolizumab Package Insert and the FDA product label.

The primary approach to grade 1 to 2 irAEs is supportive and symptomatic care with continued treatment with atezolizumab; for higher-grade irAEs, atezolizumab should be withheld and oral and/or parenteral steroids administered. Recurrent grade 2 irAEs may also mandate withholding atezolizumab or the use of steroids. Assessment of the benefit-risk balance should be made by the investigator, with consideration of the totality of information as it pertains to the nature of the toxicity and the degree of clinical benefit a given patient may be experiencing prior to further administration of atezolizumab. Atezolizumab should be permanently discontinued in patients with life-threatening irAEs.

Patients should be assessed clinically (including review of laboratory values) for toxicity prior to, during, and after each infusion. If unmanageable toxicity due to atezolizumab occurs at any time during the study, treatment with atezolizumab should be discontinued.

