|           |                               | Grade 4      | 
Permanently discontinue atezolizumab. Patient may not resume treatment, regardless of benefit.
                     Refer patient to GI specialist for evaluation and confirmation biopsy. Initiate treatment with 1-2 mg/kg/day intravenous methylprednisolone or equivalent and convert to 1-2 mg/kg/day oral prednisone or equivalent upon improvement.
                     If event does not improve within 48 hours after initiating corticosteroids, consider adding an immunosuppressive agent.
                     If event resolves to grade 1 or better, taper corticosteroids over <math>\geq 1</math> month. Resumption of atezolizumab may be considered in patients who are deriving benefit and have fully recovered from the immune-related event.
 |
|           | Pancreatitis (immune related) | Grade 2 or 3 | 
Hold atezolizumab.
                     Refer patient to GI specialist.
                     Initiate treatment with 1-2 mg/kg/day intravenous methylprednisolone or equivalent and convert to 1-2 mg/kg/day oral prednisone or equivalent upon improvement.
                     Resume atezolizumab if event resolves to grade 1 or better within 12 weeks.
                     Permanently discontinue atezolizumab and contact Medical Monitor if event does not resolve to grade 1 or better within 12 weeks.
                     For recurrent events, permanently discontinue atezolizumab and contact Medical Monitor. Patient may not resume treatment, regardless of benefit.
  |
|           |                               | Grade 4      | 
Permanently discontinue atezolizumab and contact Medical Monitor. Patient may not resume treatment, regardless of
  |

| CTCAE SOC                          | Adverse Event                             | Grade                       | Dose Adjustment and Management Recommendations  |
|------------------------------------|---|-----------------------------|---|

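### The DLT exemption for untreated nausea, vomiting or diarrhea in 7.6 has no upper grade limit, so a Grade 4 diarrhea treated with steroids alone is not automatically a DLT

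*Combined protocol and SAP*

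**What the plan says.** The last bullet of 7.6 makes other related Cycle 1 non-hematologic toxicities of Grade 3 or higher DLTs. It exempts brief, symptom-free electrolyte changes and also "nausea, vomiting or diarrhea untreated with anti-emetic support or anti-diarrheal agents, respectively". The second exemption depends only on whether the named class of drug was given. The separate laboratory exemption at the end of 7.6 is confined to Grade 3.

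In the 8.226 table, the Grade 4 row for diarrhea or enterocolitis begins "Permanently discontinue atezolizumab. Patient may not resume treatment, regardless of benefit". It goes on: "Refer patient to GI specialist for evaluation and confirmation biopsy". It then directs intravenous methylprednisolone, oral prednisone on improvement, and possibly an immunosuppressive agent if there is no improvement in 48 hours. No anti-diarrheal is named.

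Elsewhere:
- 9.3 suggests loperamide from the onset of diarrhea. At Grade 3 or 4 it permits anti-diarrheals but does not require them.
- 8.12 lists "CTCAE Grade 4 non-hematologic toxicity" as needing treatment modification. Its comparable carve-out is confined to Grade 3: "CTCAE Grade 3 nausea, vomiting, or diarrhea if manageable with antiemetic or antidiarrheal agents within 7 days would not require treatment modification".
- 8.17 says that, if treatment continues, "the anetumab ravtansine dose will be reduced after CTCAE Grade 4 nonhematologic TEAE".
- 7.2 lets investigators, in consultation with the sponsor, declare further events DLTs at their discretion.

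**The concern.** The bullet starts at Grade 3 and includes Grade 4, so an exemption without a ceiling reaches Grade 4 as well. No other bullet in 7.6 brings Grade 4 diarrhea back in. An investigator who follows the Grade 4 row exactly can therefore treat a related Grade 4 diarrhea without giving the class of drug that decides its DLT status.

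DLT counts in three to six patients per level decide the MTD. The MTD is the phase I primary endpoint (16.11) and the phase II dose (7.8). In a count that small, one event can change the decision.

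**Working it through.** **Step 1: the text, side by side.**

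| Place | Grade reached by the exemption or rule | Depends on |
|---|---|---|
| 7.6, nausea, vomiting, diarrhea | Grade 3 and above, no ceiling | No anti-emetic or anti-diarrheal given |
| 7.6, laboratory abnormalities | Grade 3 only | No clinically significant consequence |
| 8.12, nausea, vomiting, diarrhea | Grade 3 only | Manageable with agents within 7 days |
| 8.226, Grade 4 diarrhea row | Grade 4 | Steroids, then possibly an immunosuppressant; no anti-diarrheal named |
| 7.2 | Any grade | Investigator discretion |

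Read literally, a related Cycle 1 Grade 4 diarrhea managed by the Grade 4 row alone meets the 7.6 exemption.

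**Step 2: reproduce the plan's own figures.** Under 16.25 to 16.27, with true DLT rate p,

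P(escalate) = (1−p)³ + 3p(1−p)² × (1−p)³.

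At p = 0.10, 0.20, 0.30, 0.40 and 0.50 this gives 0.9061, 0.7086, 0.4943, 0.3093 and 0.1719. The table in 16.29b states 0.91, 0.71, 0.49, 0.31 and 0.17, so it reproduces.

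**Step 3: effect of one exempted event, given that it occurs, in the first three patients at dose level 1.**

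With no other DLT, leaving the event out gives 0/3 and escalation with probability 1. Counting it gives 1/3, and escalation requires no DLT in the next three patients, probability (1−p)³. With one other DLT, leaving it out gives 1/3 and probability (1−p)³; counting it gives 2/3 and no escalation.

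| p | No other DLT: left out | No other DLT: counted | One other DLT: left out | One other DLT: counted |
|---|---|---|---|---|
| 0.10 | 1 | 0.729 | 0.729 | 0 |
| 0.20 | 1 | 0.512 | 0.512 | 0 |
| 0.30 | 1 | 0.343 | 0.343 | 0 |
| 0.40 | 1 | 0.216 | 0.216 | 0 |
| 0.50 | 1 | 0.125 | 0.125 | 0 |

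**Step 4: six patients, exactly one other DLT.** Leaving the event out gives 1/6, which is tolerated. Counting it gives 2/6, which exceeds the MTD. At level 2 that moves the MTD from 6.5 to 5.5 mg/kg. At level 1 it sends the next cohort to 4.5 mg/kg.

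**Step 5: frequency.** The documents give no rate of Grade 4 diarrhea. Section 15.17 gives only an all-grade figure, 52.6%. Section 1.22 mentions one Grade 2 diarrhea among single-agent discontinuations and none among dose reductions.

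As an assumption only, suppose a share e of patients has the exempted event as the sole DLT-level toxicity. Escalation probability is then the step 2 formula at p − e:

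| p | e = 0 | e = 0.02 | e = 0.05 | e = 0.10 |
|---|---|---|---|---|
| 0.30 | 0.494 | 0.536 | 0.600 | 0.709 |
| 0.40 | 0.309 | 0.343 | 0.396 | 0.494 |

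Nothing in the documents supports choosing among these values of e.

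**The case against.** The strongest reply is that the path hardly exists in practice, and most of that reply stands.

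- The 8.226 table covers events that may be immune related and does not displace general supportive care. Section 9.1 calls for full supportive care and names anti-diarrheals. Section 9.3 suggests loperamide from onset, and the Grade 1 and 2 rows call for symptomatic treatment. A patient who worsens through lower grades will usually have had an anti-diarrheal, and the exemption then falls away.
- Grade 3 or higher colitis still counts, and the Grade 3 and 4 rows direct a biopsy. Accompanying related Grade 3 or higher dehydration or symptomatic electrolyte disturbance is a DLT in its own right.
- The class of anti-diarrheal agents is not defined, so some investigators might regard steroids as treatment.
- The phase II stopping rule in 16.622 counts related Grade 4 or higher non-hematologic events with no gastrointestinal exemption, and it includes phase I patients treated at the MTD. It does not, however, govern escalation.
- The figures in steps 3 and 4 are those of any single added DLT and are not specific to diarrhea.

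A reader might also infer that 8.12 and 8.17 prove 7.6 wrong. They do not. They govern dose changes in individual patients, and the protocol does not align those triggers with DLTs: 8.12 acts on neurotoxicity from Grade 2, while 7.6 starts at Grade 3; 7.6 counts Grade 4 platelets of any duration, while 8.11 asks for at least 7 days unless there is significant bleeding.

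Nor does the conflict over resuming atezolizumab bear on the DLT count. Section 8.21 bars resumption after "Grade 4 diarrhea or colitis", while the Grade 4 row in 8.226 ends "Resumption of atezolizumab may be considered in patients who are deriving benefit and have fully recovered from the immune-related event". That concerns rechallenge only.

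What remains is a patient who reaches Grade 4 without ever receiving an anti-diarrheal. For that patient the only way into the count is 7.2, which is permissive. For atezolizumab it asks for more frequent or more severe events than already reported, and 15.292 already describes diarrhea as potentially very severe.

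**Conclusion.** The gap is real but minor. It rests on a literal reading of 7.6, a related Cycle 1 event recorded as diarrhea, management by the Grade 4 row alone, and no use of the 7.2 discretion. The likely intent was to exempt events that had not yet had adequate supportive care, but the wording does not say so.

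Three stronger readings are not supported. The protocol does not exempt Grade 4 diarrhea in general, because any anti-diarrheal use makes the event a DLT. Grade 3 handling is not at issue: a related Grade 3 event treated with an anti-diarrheal is already a DLT as written. No comparable path is shown for nausea or vomiting, and 9.2 permits anti-emetic pretreatment, after which the patient is not untreated.

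Frequency is unknown and probably low. The consequence, if such an event occurs, is that of one missing DLT in a 3+3 design.

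**What to change.** In 7.6, insert Grade 3 immediately before "nausea, vomiting or diarrhea untreated with anti-emetic support or anti-diarrheal agents, respectively". A related Grade 4 diarrhea in Cycle 1 is then a DLT whatever supportive treatment was given. Nausea and vomiting share the phrase, so the limit applies to them too, for consistency only. Grade 3 handling stays as it is.

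The cost is a short amendment with no new procedures. A cohort may occasionally expand from three to six patients, or the MTD may come out one level lower. The planned three to six patients per level already allows for the expansion.
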